Study Design	
This is an open-label, randomized, two-stage clinical study. During Stage 1, 26 patients will be randomized into each of the 2 treatment arms (52 patients total) stratified by prior response to venetoclax in combination with azacytidine or decitabine:
 
• Refractory (ie, failed to achieve a CR/CRI or achieved a CR/CRI with duration <90 days)• Relapsed (ie, reoccurrence of disease following a CR/CRI with duration ≥ 90 days). 
Lead-in Cohort
 
As an additional safety measure given the unique patient population and outpatient treatment administration, a separate lead-in cohort of approximately six patients (at least three patients in each treatment arm) will be enrolled, treated, and evaluated for dose-limiting toxicities (DLTs). If a DLT is observed, dose de-escalation will occur as outlined in Appendix F. Should no additional DLTs be observed during Cycle 1, Amendment 2 be approved, and the Data Safety Monitoring Board (DSMB) confirm safety, randomization into Stage 1 will commence as outlined in the protocol. However, should an additional DLT be observed at Dose Level 1, a clinical meeting would be scheduled to discuss the utility/futility of continuing the study as currently designed.
 
If patients treated in the lead-in cohort are still on study when Amendment 2 is approved and the DSMB has confirmed safety, they may be permitted to shift to the higher alvocidib (ALV) dose regimen, ie, ALV 50 mg/m² IV bolus, per investigator discretion.
 
Stage 1
 
A futility analysis will be conducted at the end of Stage 1 to determine if the combined CR rate meets the threshold for continuing the study. Using an alpha spending function to control the overall level of significance, the threshold is that the one-sided p-value be <0.60525 in order to initiate Stage 2; which is achieved if there are more than 4 combined CRs among the 52 Stage 1 patients. No additional patients will be enrolled if the number of patients with combined CR at the end of Stage 1 fails to meet this criterion.
 
Stage 2
 
Determination of the recommended alvocidib-based treatment arm for Stage 2 will be subjective, comparing the response rates, relative safety, and the risk-benefit ratio of the two Stage 1 treatment arms. An additional 76 patients will be enrolled into the treatment arm selected for Stage 2 for a total of 102 patients (26 and 76 from Stages 1 and 2, respectively). The combined CR rate (primary

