4.5.1.1 Hyperkalemia and Tumor Lysis Syndrome

Tumor lysis may occur as part of initial cytoreductive therapy. The most extreme form, known as Tumor Lysis Syndrome (TLS), is characterized by hyperkalemia, hyperuricemia, hyperphosphatemia, increased lactate dehydrogenase (LDH), coagulopathy, and a potential cytokine release

syndrome. ***Due to an increased likelihood of TLS, hospitalization of patients with monocytic differentiation and/or a peripheral blast count of >10,000/mm³ is strongly recommended for the first dose of alvocidib (ie, Cycle 1 / Day 1).***

- Mandatory IV hydration with 0.45% NaCl (or similar hydration fluid per institutional standard) sterile solution at **250-500 cc** for 1-2 hours prior to alvocidib, then an additional **250-500 cc** for 1-2 hours after alvocidib during Cycle 1 (optional for subsequent cycles for patients who have achieved a CR).
- Replacement of excessive fluid losses, including from diarrhea, should be done unless otherwise clinically indicated.
 - Alvocidib is known to induce mild diarrhea during treatment days. Over-the-counter measures are typically effective in this setting if initiated early. Persistent diarrhea despite optimal outpatient management would trigger medical consultation. Early consideration should be given for possible *Clostridioides difficile* (*C. difficile*) infection in this patient population and identifying/treating as expeditiously as possible should be top of mind (see [Section 4.5.1.2](#)).
- Mandatory oral allopurinol to be started at least 72 hours prior to Day 1 of Cycle 1 and continued until completion of the first cycle (ie, 28 days). This may be discontinued for subsequent treatment cycles if uric acid levels are within normal limits and there is no evidence of TLS.
- Mandatory oral phosphate binder to be started at the same time as initiation of IV hydration on Day 1 of Cycle 1 and continued for the first week (ie, 7 days).
 - If serum phosphorus levels are <3 after the first treatment with alvocidib and there is no evidence of TLS, phosphate binders may be discontinued. Patients should continue to be monitored for TLS as outlined for subsequent treatment cycles. Caution is warranted for patients who still have a high blast count as they remain at risk for TLS with subsequent treatments.
- Evaluation of laboratory indicators of TLS during initial therapy (may be adjusted for subsequent cycles based on extent of tumor burden):

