5.3 Cycles 2+

Patients who achieve CR, CRi, CRh, MLFS, PR, or clinical benefit after the first cycle (completion of all doses) may receive additional optional cycles of treatment until disease progression (in the event of toxicities see the recommendations in [Table 3](#), if applicable).

Those who achieve a CR, CRi, CRh, or MLFS (ie, <5% blasts in bone marrow) should not be given **subsequent cycles** until ANC >0.5 and platelets >50. If treatment is delayed >2 weeks for cytopenias, a bone marrow biopsy should be performed to reassess disease status.

Patients not demonstrating evidence of CR, CRi, CRh, MLFS, PR, or clinical benefit after 4 cycles of treatment will be considered for removal from the study, although with permission of the Medical Monitor, treatment may continue if clinically indicated (in the event of toxicities see the recommendations in [Table 3](#), if applicable).

There is a maximum limit of 6 weeks between the start of cycles unless otherwise discussed with the medical monitor.

5.3.1 Cycles 2+: At Least 2 Hours Prior to First Dose (± 3 days)

During Cycles 2+, pretreatment IV hydration, oral allopurinol, and oral phosphate binder may be discontinued if serum uric acid and phosphorus levels are within normal limits and there is no evidence of TLS.

Should TLS be suspected during subsequent cycles, perform the following procedures at least 2 hours prior to starting therapy on Day 1 (unless otherwise stated):

- Initiate supportive care measures prior to first dose in all patients to minimize the likelihood of TLS:
 - Administer pretreatment IV hydration and determine if oral allopurinol and oral phosphate binder are still clinically indicated (see [Section 4.5.1](#))

- Assess patient for adequate hydration at all study visits and replace excessive fluid losses, including from diarrhea, unless otherwise clinically indicated ([Section 4.5.1.2](#) and [Section 4.5.1.3](#))
- Review study diary and remind patient to bring diary back at next clinic visit

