APPENDIX A – SCHEDULES OF ACTIVITIES
Arm 1 (ALDAC): Schedule of Activities

TESTS/PROCEDURES	SCREENING												ALL TREATMENT CYCLES (CYCLE = 28 DAYS)													
	-14 days	-72 hours	D1	D2	D3	D4	D5	D6	D7	D8	D9	D10	D11	D12	D15	D22	D28	EOT	FU							
Visit window		±3d C2+																								
Obtain ICF	X																									
Medical history	X																									
Full PE	X																									
Abbreviated PE																										
BSA																										
Weight (kg)	X																									
Height (cm)	X																									
ECOG	X																									
Vital signs	X																									
Bone marrow & peripheral blood	X																									
Cytogenetic profiling	X																									
12-lead ECG	X																									
Pregnancy test	X																									
Hematology	X	X	X C2																							
Full chemistry panel	X	X	X C2+																							
Pre-infusion TLS labs				X																						
Post-infusion TLS labs				Only C1																						
Coagulation				X Only C1	X Only C1																					
Urinalysis				X C2+*																						
Blood transfusions																										
Lumbar puncture for CNS disease	X*																									
Review Inc/Exc Criteria		X																								
Daily oral allopurinol																										
IV hydration pre & post infusion																										
Oral phosphate binder																										

twice a week during the 10 day LDAC injections

twice a week during the 10 day LDAC injections

Recorded from 56 days prior to first study treatment dose, through 56 days after last dose of study treatment

Mandatory from 72 hours prior to D1 up to C1D28. As clinically indicated for subsequent cycles.

For C1, mandatory

X C2+***

TESTS/PROCEDURES	ALL TREATMENT CYCLES (CYCLE = 28 DAYS)																		
	-14 days	-72 hours	D1	D2	D3	D4	D5	D6	D7	D8	D9	D10	D11	D12	D15	D22	D28	EOT	FU
Visit window		±3d C2+																±3d	±5d
Assess patient's hydration level																			
Prophylactic antibiotics, antifungals per site SOC																			
Antiviral per site SOC																			
Alvocidib infusion																			
LDAC injection																			
Provide / review patient diary																			
Con meds																			
Assessment of AEs																			
Phone call to patient																			

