APPENDIX F – DOSE DE-ESCALATION PLAN

Alvocidib and cytarabine have been administered together in patients with AML at a variety of dosages and schedules. The plan detailed below will guide dose modifications, if needed, in the proposed patient population. The proposed starting doses of alvocidib are approximately one-fourth of the typical starting doses administered in historical studies in patients with hematologic malignancies, but to confirm that they are tolerable in this patient population, dosing will initially commence with a 6-patient lead-in cohort comprised of 3 patients in each treatment arm (ie, Dose Level 1).

Three patients in each arm of the lead-in cohort may be enrolled and treated simultaneously. In the absence of any dose-limiting toxicity (DLT), **approval of amendment 2, and with recommendation of the DSMB**, the study will proceed as outlined and randomization **into Stage 1** will begin into Arm 1 or Arm 2. If a patient in the lead-in cohort experiences a DLT during the first cycle, then the alvocidib doses for that patient will be reduced by 25% (ie, Dose Level -1) as shown in the table below. That arm of the lead-in cohort will be expanded by at least one patient to determine whether the event was isolated in nature. If no additional DLTs are observed, the study will proceed as outlined. Once all 6 patients have been treated in the lead-in cohort with ≤ 1 DLT observed, patients will be accrued and randomized into Arm 1 or Arm 2 **of Stage 1**. However, should ≥ 2 patients in a lead-in arm experience a DLT, a clinical meeting would be scheduled to discuss the utility/futility of continuing the study as currently designed.

Stage 1	Study Drug Component	Dosing Days	Dose Level 1	Dose Level -1 ^a
Arm 1	Alvocidib ^b	1	25 mg/m ² ^c IV bolus	19 mg/m ² IV bolus
	Cytarabine	3 through 12	20 mg/m ² SC injection	20 mg/m ² SC injection
	Alvocidib ^b	15	50 mg/m ² IV bolus	39 mg/m ² IV bolus
Arm 2	Alvocidib ^b	1	25 mg/m ² ^c IV bolus	19 mg/m ² IV bolus
	Alvocidib	8, 15	50 mg/m ² IV bolus	39 mg/m ² IV bolus

a Dose Level -1 to be used should a DLT be observed in the lead-in cohort of 6 patients (3 patients/treatment arm)

b Alvocidib to be administered as an IV bolus over 30 to 60 minutes

c 25 mg/m² during Cycle 1, Day 1; 50 mg/m² during Cycles 2+, Day 1 after completion of safety lead-in cohort, **approval of amendment 2, and with recommendation of the DSMB**.

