A DLT is defined as any one of the following events observed within Cycle 1, regardless of Investigator attribution:

- Any Grade 5 toxicity that is not clearly and incontrovertibly related to the underlying disease or extraneous causes
- Grade 4 neutropenia **or thrombocytopenia** lasting ≥ 42 days from start of cycle in absence of evidence of **morphologic disease ($\leq 5\%$ blasts) and/or evidence of disease by flow cytometry, FISH, or cytogenetics**

- Grade ≥ 3 tumor lysis syndrome or related electrolyte disturbances (hyperkalemia, hypophosphatemia, hyperuricemia) that do not resolve to \leq Grade 2 within 14 days
- Grade ≥ 3 elevations in creatinine that do not resolve to \leq Grade 2 within 7 days
- Any AST and/or ALT elevation $\geq 3 \times$ ULN accompanied by serum bilirubin levels $>2 \times$ ULN is suggestive of possible drug-induced liver injury (ie, liver function test abnormalities meeting Hy's Law criteria) and should be considered a DLT regardless of duration ***unless an alternative etiology is more likely***
- Grade 3 or 4 nonhematologic AEs will be considered dose limiting, regardless of duration, with the exception of Grade 3 – 4 nausea, vomiting, diarrhea, and electrolyte imbalances unless persisting for more than 48 hours despite optimal medical management (in which case they will be considered DLTs)
- Dosing delays >1 week due to treatment-emergent adverse events (TEAEs) or related severe laboratory test values.

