2. OVERVIEW OF STUDY DESIGN

Experimental Design:

This is an open-label, randomized, two-stage clinical study. During Stage 1, patients will be randomized in a 1:1 treatment allocation into one of two treatment arms:

- Arm 1: ALDAC (Alvocidib + Low-dose cytarabine)
- Arm 2: ALV (Alvocidib)

stratified by prior response to venetoclax in combination with azacytidine or decitabine:

- Refractory (i.e., failed to achieve a CR/CRI or achieved a CR/CRI with duration <90 days. OR
- Relapsed (i.e., reoccurrence of disease following a CR/CRI with duration ≥ 90 days).

This study will be divided into three main parts:

1. Lead-in Cohort

Current Status: Based on a review of data (n=7 patients) from the safety lead-in cohort, the Data Safety Monitoring Board (DSMB) granted unconditional approval to continue enrollment (reference DSMB Recommendation Form dated 11 Sep 2020) into the TPI-ALV-202 clinical trial.

Planned: As an additional safety measure given the unique patient population and outpatient treatment administration, a separate lead-in cohort of approximately six patients (at least three patients in each treatment arm) will be enrolled, treated, and evaluated for dose-limiting toxicities (DLTs). If a DLT is observed, dose de-escalation will occur. Should no additional DLTs be observed during Cycle 1 and the Data Safety Monitoring Board (DSMB) confirm safety, randomization into Stage 1 will commence as outlined in the protocol. However, should an additional DLT be observed at Dose Level 1, a clinical meeting would be scheduled to discuss the utility/futility of continuing the study as currently designed.

[figure not shown]
If the DSMB has confirmed safety, patients may be permitted to shift to the higher alvocidib (ALV) dose regimen, i.e., ALV 50 mg/m² IV bolus, per investigator discretion.

Stage 1

Current Status: As of November 17, 2020, 4 patients were enrolled in Stage 1.

Planned: A futility analysis will be conducted at the end of Stage 1 to determine if the combined CR rate meets the threshold for continuing the study. Using an alpha spending function to control the overall level of significance, the threshold is that the one-sided p-value be <0.60525 in order to initiate Stage 2, which is achieved if there are more than 4 combined CRs among the 52 Stage 1 patients. No additional patients will be enrolled if the number of patients with combined CR at the end of Stage 1 fails to meet this criterion.

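### Appendix F's cytopenia DLT needs 42 days, but DLTs are counted in a 28-day Cycle 1 and no text makes Stage 1 wait for Day 42

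*Protocol*

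**What the plan says.** Appendix F of the protocol introduces its list with "A DLT is defined as any one of the following events observed within Cycle 1, regardless of Investigator attribution". The cycle length is given consistently: the Appendix A schedules are headed "ALL TREATMENT CYCLES (CYCLE = 28 DAYS", Section 4.4.2 repeats dosing every 28 days, and Section 4.5.1.1 has allopurinol "continued until completion of the first cycle (ie, 28 days".

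One bullet in the list is specific to cytopenia. It makes Grade 4 neutropenia or thrombocytopenia a DLT when it has lasted at least "42 days from start of cycle in absence of evidence of" disease, whether morphologic or by flow cytometry, FISH or cytogenetics.

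Entry to Stage 1 is described in five places. The synopsis, Section 4.1 and Section 4.4.2 use "Should no additional DLTs be observed during Cycle 1", together with approval of Amendment 2 and DSMB confirmation. SAP Section 2 has "Should no additional DLTs be observed during Cycle 1 and the Data Safety Monitoring Board (DSMB) confirm safety". Appendix F puts it as "Once all 6 patients have been treated in the lead-in cohort with" no more than one DLT.

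Section 5.3 bears on how long Cycle 1 can last: "There is a maximum limit of 6 weeks between the start of cycles unless otherwise discussed with the medical monitor".

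**The concern.** The window and the event do not fit together. A DLT must be seen in Cycle 1, and the cytopenia DLT cannot be established until two weeks after a 28-day Cycle 1 has ended. The texts on opening Stage 1 point to Cycle 1, or to patients having been treated, and not to Day 42.

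The patient who matters is narrowly defined: in the lead-in, with Grade 4 neutropenia or thrombocytopenia still running, no evidence of disease, and Day 42 not yet reached when the decision is taken. Appendix F lets three patients per arm be treated at the same time, so nothing guarantees that the later patients are near Day 42.

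A single event changes the action. Under Appendix F, one DLT cuts that patient's alvocidib dose by 25% and expands the arm by at least one patient; two or more in an arm lead to a clinical meeting. The lead-in is also the last point for de-escalation: dose reductions are barred afterwards (Table 3, Figure 1 footnote), while Day 1 alvocidib rises from 25 to 50 mg/m² in Cycles 2+.

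Prolonged neutropenia is a known effect of the drug in combination. Section 2.6.2.1 reports that neutropenia of more than 40 days was dose-limiting with bolus FLAM at 60 mg/m²/d.

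**Working it through.** No alpha, power or sample-size figure depends on this point. The check is day arithmetic on the protocol's own numbers.

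**Inputs.** DLT window: Cycle 1 (Appendix F). Cycle length: 28 days (Appendix A, Sections 4.4.2 and 4.5.1.1). Cytopenia threshold: 42 days from the start of the cycle (Appendix F). Day 28 visit window: ±3 days (Section 5.2.6). Limit between cycle starts: 6 weeks (Section 5.3).

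**Gap = 42 − last day of the DLT window.**

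1. *Literal reading, Cycle 1 ends at Day 28.* 42 − 28 = 14 days. With the visit window: 42 − 31 = 11 and 42 − 25 = 17 days.
2. *Cycle 1 runs until Cycle 2 starts.* Section 5.3 holds the next cycle in a patient with fewer than 5% marrow blasts until ANC is above 0.5 and platelets above 50. The weekly visits during a delay sit under a Cycle 1 heading (Section 5.2.5). At the limit, 6 × 7 = 42 and 42 − 42 = 0 days. This needs a held Cycle 2, so it does not fit a patient who stops after Cycle 1.
3. *The event starts in Cycle 1 and is judged on its own 42-day clock.* The bullet is then coherent and covers a patient who stops after Cycle 1. The DLT can be met, but only at Day 42, and the text on opening Stage 1 is unchanged.

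**Do other provisions force the wait?**

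- *Dosing-delay DLT (more than 1 week).* Cycle 2 is due on Day 29, and 29 + 7 = 36, so a late Cycle 2 qualifies only after Day 36. That is past Day 28 and under the same Cycle 1 limit.
- *Cycle 2 hold (Section 5.3).* It stops that patient's dosing, not the opening of Stage 1.
- *Marrow biopsy after a cytopenia delay of more than 2 weeks (Section 5.3).* 29 + 14 = 43, so it applies after Day 43.
- *SAE rule (Section 8.3).* It starts at Day 42, uses a different criterion (marrow cellularity below 5%), and triggers 24-hour reporting (Section 8.5), not a hold.
- *Adverse event follow-up (Section 6.3).* It covers a patient who has stopped treatment but has no link to the Stage 1 decision.
- *DSMB confirmation.* This is a real condition, but no text tells the DSMB to wait for Day 42.

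**The case against.** The best counter-argument is reading 3. The bullet states its own horizon, and others in the list work the same way: tumor lysis not resolving within 14 days, creatinine not resolving within 7. A Grade 3 creatinine rise on Day 25 could not be judged until 25 + 7 = Day 32 either. Section 5.3.5 calls for a marrow when cytopenias have lasted 42 days from prior cycles, and Section 8.3 uses the same Day 42 clock. So the protocol does follow cytopenia beyond the cycle in which it began.

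This stands as a sensible interpretation, and it removes any claim that the bullet is meaningless. It leaves the waiting rule unwritten. The parallel is also incomplete: the 7- and 14-day bullets overrun Day 28 only when onset is late, whereas the 42-day bullet always does.

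A second objection is that Stage 1 would hardly open on Day 28 exactly. DSMB review takes time, data entry may take 5 days and query answers 3 (Section 10.1), and a nondiagnostic marrow is repeated within 7–10 days. That is fair: 14 days is a nominal figure, and the practical gap may be shorter or nil. But none of these is a requirement to wait.

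Third, the risk is probably lower than the FLAM experience suggests. That regimen was more intensive, and diarrhea was the dose-limiting toxicity of alvocidib monotherapy (Section 2.8). This also stands.

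A reader might go further and infer that the cytopenia DLT could never be counted, or that Stage 1 was opened over an unrecognised DLT. The documents support neither. Readings 2 and 3 allow it to be counted. SAP Section 2 records that the DSMB reviewed 7 lead-in patients and approved continuation without conditions (form dated 11 Sep 2020), and no patient-level cytopenia data are given.

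**Conclusion.** The concern holds as a gap in the written rule. On the literal reading the cytopenia DLT lies a nominal 14 days outside its own window (11 to 17 with the Day 28 visit window). On the two more generous readings it can be met. On all three, no text expressly keeps Stage 1 closed until Day 42.

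The conclusion assumes a lead-in patient (about six planned, 7 enrolled) with ongoing Grade 4 cytopenia and no evidence of disease, less than 42 days from Day 1 at the decision. The documents do not say how many such patients there were, if any. No day range can usefully be set for the End of Treatment visit of a patient who stops after Cycle 1: visit windows and the date of the decision move it to either side of Day 42 (a Day 31 decision allows 31 + 14 = Day 45).

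The practical weight is modest. The lead-in decision is past, and the sponsor closed the study on 17 November 2020 with 4 Stage 1 patients (SAP Section 1). The point concerns the rule as planned. It was still worth correcting, because the protocol chose to make prolonged cytopenia a lead-in DLT and did not say when it must be judged.

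**What to change.** Put the following in Appendix F and in the text on opening Stage 1 (synopsis, Sections 4.1 and 4.4.2), and align SAP Section 2:

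*The DLT window is Cycle 1 (28 days), extended to Day 42 from the start of Cycle 1 for any lead-in patient with ongoing Grade 4 neutropenia or thrombocytopenia and no evidence of disease. Hematology continues weekly to Day 42 in these patients, including those who stop treatment after Cycle 1. Stage 1 does not open until each such patient has recovered, shown evidence of disease, had a DLT, or reached Day 42.*

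The cost is wording, about two extra blood counts per affected patient (14 days at weekly intervals), and a delay to Stage 1 of up to about two weeks. Beyond the wording, the cost arises only if such a patient exists.

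Since the study is closed, what remains is to state in the synoptic report which DLT window was applied, and to use the corrected rule in any later protocol.
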